STEP 3 – **Identification of patients exposed to anifrolumab for the outcome-specific source** population

At step 3, the malignancy and serious infection source populations will be created.

Step 3a. Exposed patients in the malignancy source population

Additional exclusion criteria to be applied to the exposed patients:

• A diagnosis of any malignancy prior to index date.

³ According to the SLE severity algorithm, most moderate to severe patients will be those with a previous exposure to SOC indicated for moderate to severe disease. A very small group of patients, defined as having moderate/severe SLE based on the existence of SLE-related comorbidities, will not have a prescription of SOC for moderate/severe SLE.

Step 3b. Exposed patients in the serious infection source population

Additional exclusion criteria to be applied to the exposed patients:

- A diagnosis of any malignancy prior to index date.
- A diagnosis of HIV/AIDS or congenital immunodeficiency prior to index date.
- Organ or bone marrow transplant procedure prior to index date.
- A diagnosis of serious infection in the previous 6 months.

STEP 4 – **Time-based exposure sets**

This step is defined to create the time-based exposure sets, from the outcome-specific source populations. For each patient exposed to anifrolumab (identified in steps 3a and 3b) all unexposed patients from the source population (step 2b) that meet the following criteria will be included as unexposed patients.

Step 4a. Malignancy time-based exposure set

Patients exposed to anifrolumab from the malignancy source population (step 3a) and patients unexposed to anifrolumab (step 2b). Inclusion criteria for patients unexposed to anifrolumab (exposed to SLE SOC):

- At least a prescription of SOC indicated for moderate to severe SLE (Table 14).
- Duration of the previous exposure to SLE SOC similar to the SLE SOC duration of the corresponding exposed patient (+/- 45 days [wider time intervals may be considered if matches cannot be obtained using this time window]), at index date. The **index date** for the patient unexposed to anifrolumab will be the SLE SOC prescription date that will result in length of the SLE SOC treatment closer to SLE SOC treatment of the corresponding exposed patient.
- No prescription for anifrolumab prior to index date.
- A minimum data availability of 12 months prior to index date.
- Age ≥ 18 years at index date.

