10.3.3 Participants' characteristics and potential confounders/risk factors

The variables presented in Table 6 will be considered to describe the cohorts' characteristics (objective 5), as selection criteria or as adjustment variables for confounding control. The final choice of characteristics, risk factors and confounders will depend on the availability of data (e.g., malignancy family history) and clinical relevance. After feasibility assessment, ethnicity was excluded as a covariate since it was not available in any of the data sources (Table 26). Specific definitions will be presented in detail in the SAP.

At baseline, the variables presented in Table 6, will be considered to create the PS, since they may influence the decision of prescribing anifrolumab or other SLE SOC drugs and are considered potential risk factors for each outcome. Confounding variables will be retrieved at index date or in the look-back period as presented in Figure 2 and Figure 3.

In the following sections, specific confounders for malignancies will be presented, followed by serious infections confounders and SLE disease severity and activity. A summary of the variables for each cohort is presented in Table 6.

	Study	cohort
	Serious infections	Malignancies
Demographic characteristics		
Cohort entry year	✓	✓
Age	✓	✓
Sex	✓	✓
Socioeconomic status (including education)	✓	✓
Lifestyle characteristics		
Smoking	✓	✓
Alcohol/substance abuse	✓	✓
Height, weight, or body mass index (kg/m ²)	✓	✓
General Medical History		
Comorbidities relevant for SLE patients (Table 20)	✓	✓
Malignancy family history		✓
Procedures with radiation exposure		✓
Prior virus/infections (risk factors for malignancies) (Table 22)		✓
Previous infection (serious and non-serious infection)	✓	
Vaccines and passive immunity drugs (Table 23)	✓	
Comedication [polypharmacy] (Table 24)	✓	✓
SLE disease history and profile		
Disease duration, months (time from diagnosis to study entry)	✓	✓
Disease severity components	~	✓
Disease activity	✓	✓
SLE standard of care (Table 14)	✓	✓

Table 6 Participant characteri	stics and confounding	variables for	each study cohort:
malignancy and serious infection	7		-

Abbreviations: SLE, systemic lupus erythematosus.

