10.3.3.1 Potential confounders for the malignancy cohort

For the analysis of malignancies, potential confounders include demographics and lifestyle characteristics (as presented in Table 6), SLE history (including SLE severity, activity as detailed below) and other clinical characteristics. Some infections may be important risk factors for specific types of malignancies [6, 63] (Table 22), such as Human Papillomavirus (HPV) infection and the risk associated with cervical cancer [84] or the emergence of the oncogenic Epstein-Barr virus. HPV vaccine will be considered as reducing the risk of cervical, oropharyngeal, and anal cancer occurrence.

⁷Some data sources may not have available some of the relevant variables.

Comorbidities recognised as risk factors for cancer development will be considered, namely cardiovascular diseases [44, 45], diabetes [94], liver disease [87], kidney disease [86], chronic respiratory disease [25, 55], among others (Table 20). Likewise, several drugs have been associated with changes in the risk of cancer and will be included as covariates, namely antidiabetics [91], antihypertensives [20], antihrombotic agents [43, 53] and other recognised carcinogenic drugs (Table 24).

Furthermore, increased inflammatory activity is purported to be associated with malignancy risk. In addition to considering SLE severity and activity, other comorbidities may increase inflammatory status, namely other autoimmune diseases (excluding SLE), acquired immunodeficiencies, and chronic infections. Exposure to specific SLE drugs, such as prednisolone, cyclophosphamide, rituximab, azathioprine or cyclosporin, has also been purported to be associated with cancer development [3, 11, 100]. Adjustment for prior use of cyclophosphamide or rituximab are already taken into account when controlling the SLE severity as these drugs are used to define severe SLE. Within the group of other immunosuppressants, recognised carcinogenic drugs will be considered separately.

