	Pleuritis [51]	A15.6, A15.7, A16.5, A16.7
	Thrombocytopenia [51]	D69.6, D69.5, D69.4
Other comorbidities	Autoimmune diseases excluding SLE (e.g., rheumatological, inflammatory bowel disease and multiple sclerosis) [101] Immunodeficiencies (excluding congenital and HIV) [30]	L40, I73.0, M15.0, M35.0, K50, K51, G35 D80-D89
	Cardiovascular diseases (atrial fibrillation, coronary artery disease, hypertension) [46, 67, 81]	I48, I25.1, I10-I15
	Chronic respiratory diseases [30, 35, 67, 101]	J40-J47
	Gastrointestinal conditions (e.g., peptic ulcer disease, gastro- oesophageal reflux disease, dyspepsia, helicobacter pylori infection, Barrett's oesophagus, gastritis and duodenitis, chronic pancreas disease, chronic liver disease, gallstones)	K21, K22.7, K25-K29, K30, K76.9, K80-K82, K86, B98.0

Abbreviations: HIV, human immunodeficiency virus; ICD-10, international statistical classification of diseases tenth revision.

*Three variables were removed from the index because they are exclusion or censoring criteria: HIV, metastatic disease, any malignancy.

Table 21 Exemplar code list for SLE-related comorbidities (SLE severity and activity algorithms)¹¹

	Group	Conditions	ICD-10 codes
Moderate comorbid	Cardiovascular	Haemolytic anaemia	D55-D59
conditions	cardiorespiratory system	Myocarditis	I40
		Pericarditis	I30
		Pleurisy/pleural effusion	J90 J91
		Vasculitis (excluding aortitis)	M05.2
	Hepatic and	Acute pancreatitis	K85
	gastrointestinal	Hepatitis (non-viral)	K72.0
		Lupus enteritis/colitis	
	Musculoskeletal	Avascular ischaemic necrosis of bone	M87
	Neurological	Demyelinating syndrome/acute inflammatory demyelinating	G36-G37
		polyradiculoneuropathy	
		Mononeuropathy/polyneuropathy	G56-G64
		Myelopathy	G99.2
		Pseudotumor cerebri	G93.2
		Seizure	R56.8
	Renal	Nephritis	N10, N11
		Renal impairment (other than nephritis or end-stage renal disease)	S37.0, N18 (excl. N18.5)
	Ocular	Chorioretinitis	H30.9
		Episcleritis/scleritis	H15
Severe comorbid	Cardiovascular	Aortitis	I79.1
conditions	cardiorespiratory system	Arterial/venous thrombosis	I82
		Cardiac tamponade	I31.9
		Pulmonary haemorrhage	R04.8
		Stroke (cerebral infarction)	I63
		Transient ischaemic attack	G45
	Hepatic and gastrointestinal	Intestinal pseudo-obstruction	K56.0
	Neurological	Acute confusional state/psychosis	F05.1, F05.9
		Aseptic meningitis	G02.0, A87.0, G01
		Cranial neuropathy	S04

¹¹SLE severity and severity algorithms defined in Section 10.3.3.3 [39, 56].

	Group	Conditions	ICD-10 codes

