	Ocular	Optic neuritis	H46
	Renal	End-stage renal disease	N18.5
		Renal failure	N17, N19
Additional conditions	Other	Arthritis/arthralgia	M25.5
to be considered to		Dry eye/tear film insufficiency	H04.1
define moderate and		Rash	R21
severe flares (SLE activity algorithm	Low white blood cell count (leukopenia, neutropenia, lymphocytopenia)	R72	
only)		Lymph node enlargement	R59
		Myalgia/myositis	M79.1
		Urticaria	L50

Abbreviations: ICD-10, international statistical classification of diseases tenth revision.

Prior infection diagnosis	ICD-10 codes
Epstein-Barr virus	D82.3
Hepatitis B virus	B16
Hepatitis C virus	B17.1, B18.2
HIV	B20-B24
HTLV-I	B33.3, G04.1, Z22.6, B97.3
Human papillomavirus	B97.7
Kaposi's sarcoma herpesvirus	C46

Abbreviations: HIV, human immunodeficiency virus; HTL V-I, human T-cell lymphotropic virus type 1; ICD-10, international statistical classification of diseases tenth revision.

¹² virus/infections considered risk factors for malignancies [6, 63].

Table 23 Exemplar code list of vaccines and immunoglobulins¹³

	ATC codes		
Haemophilus influenzae B	J07AG		
Hepatitis A and hepatitis B	J07BC		
Herpes zoster	J07BK		
Human papillomavirus*	J07BM		
Influenza	J07BB		
Meningococcal C	J07AH07		
Pneumococcal	J07AL		
Severe acute respiratory syndrome coronavirus 2	J07BX03		
Immunoglobulins, normal human	J06BA		
Specific immunoglobulins (e.g., varicella/zoster, hepatitis A, measles	J06BB (except J06BB01: anti-D (rh)		
immunoglobulins)	immunoglobulin)		
Antibacterial monoclonal antibodies: raxibacumab, bezlotoxumab	J06BC02, J06BC03		
Antiviral monoclonal antibodies (palivizumab; motavizumab;			
tixagevimab and cilgavimab; nirsevimab**; casirivimab and	J06BD		
imdevimab**)			

Abbreviations: ATC, anatomical therapeutic chemical.

*For the malignancy cohort this is the only vaccine to be considered. ** No ATC code is available at the moment (August 2022).

¹³ Recommended vaccines for SLE patients [54, 93].

Table 24 Exemplar code list of comedication polypharmacy

Comedication	SI	Malignancies	ATC codes
Agents acting in the renin-angiotensin system		x	C09
Alkylating agents (excluding cyclophosphamide)		x	L01A (excluding L01AA01)
Anabolic agents for systemic use		x	A14
Antiepileptics		x	N03
Antihypertensives		x	C02
Antiobesity preparations, excl. diet products		X	A08
Antithrombotic agents		x	B01, A01AD05, N02BA01
Aspirin (acetylsalicylic acid)		X	A01AD05, B01AC06, N02BA01, M01BA03
Beta blocking agents		x	C07
Bisphosphonates		x	M05BA, M05BB

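### Table 22 (cancer-risk infections): three of seven rows need recoding. One is empty by construction, one uses a code from the immunodeficiency block, and one has no chronic hepatitis B code

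*Protocol*

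**What the plan says.** Protocol section 10.3.3.1 introduces the covariates: "Some infections may be important risk factors for specific types of malignancies [6, 63] (Table 22"; it names Epstein-Barr virus in the same sentence. Table 6 ticks the item "Prior virus/infections (risk factors for malignancies) (Table 22" for the malignancy cohort only, and section 10.3.3 states: "At baseline, the variables presented in Table 6, will be considered to create the PS".

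The three rows of Table 22 (Appendix 3) at issue are:

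- "Kaposi's sarcoma herpesvirus", with the single code C46
- "Epstein-Barr virus D82.3"
- Hepatitis B virus, with the single code B16. The next row, hepatitis C, has B17.1 and B18.2.

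The other rows are HIV, HTLV-I and human papillomavirus.

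Three other places bear on these codes. Table 15 gives the overall malignancy range as C00-C96 plus D00-D09. Section 10.2.2.1 excludes patients with "A diagnosis of any malignancy prior to index date", for exposed patients at step 3a and for unexposed patients at step 4a. Table 20 assigns D80-D89 to the covariate "Immunodeficiencies (excluding congenital and HIV) [30]".

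Appendix 3 calls its lists exemplar and leaves their final form to the SAP. Section 10.3 says the same codes will be adapted to each source's coding system.

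**The concern.** A confounder is adjusted for only if its code finds the patients who have it. Here one code can find nobody in the cohort, one is filed under a different kind of condition, and one appears to cover only part of the disease.

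The plan's own safeguard would not reveal this. Balance is judged by standardised differences (section 10.7.1.2), and only variables left imbalanced enter the outcome model (section 10.7.1.4). A covariate that is zero in both groups can never look imbalanced. Its standardised difference is zero over zero, so it is undefined, and a table showing 0 or a blank would suggest control of something never measured.

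Germany and Spain are analysed by the data providers (section 10.6), so an uncorrected code would be carried into analyses run elsewhere.

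**Working it through.** No sample size or power figure is involved. The check sets Table 22 against the protocol's other code lists and its exclusion criteria.

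**1. Kaposi's sarcoma herpesvirus, C46.**
- C46 lies within C00-C96 (Table 15).
- Any malignancy before index is excluded in both groups, with no time limit (steps 3a and 4a). The covariates are taken at index or in the look-back period (section 10.3.3).
- A patient with C46 before index therefore cannot be in the cohort, and the covariate is 0 for everyone. The only gap is a code dated exactly on the index date. Once malignancy follow-up has started, C46 is an outcome.
- The protocol applies this logic elsewhere. The Table 20 footnote drops three variables from the SLE risk index because they are exclusion or censoring criteria, and any malignancy is one of them. Table 22 did not get the same check.

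**2. Epstein-Barr virus, D82.3.**
- D82.3 lies within D80-D89, which Table 20 labels immunodeficiencies.
- On the protocol's own labelling the row is not an infection code, and it overlaps a Table 20 covariate.
- Table 17 uses the B27 block for an infection (B27.1, cytomegaloviral mononucleosis), but no B27 code is given for Epstein-Barr virus.

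**3. Hepatitis B, B16.**

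| Row in Table 22 | Codes | Acute and chronic both covered? |
|---|---|---|
| Hepatitis C | B17.1, B18.2 | Yes: Table 17 labels B17.1 acute and B18.2 chronic |
| Hepatitis B | B16 | No code from the B18 block, where chronic hepatitis C sits |

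- Section 10.3.3.2 names hepatitis B as an example of a chronic infection.
- The liver disease codes in Table 20 (K70-K77) contain no B18 code and do not fill the gap.
- The row still finds B16 cases, so it is incomplete, not empty.

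**Count.** 3 of 7 rows are affected: 1 empty, 1 in the wrong block, 1 under-captured. 7 − 3 = 4 are not challenged.

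**Illustration of size (assumed inputs, none from the protocol).** For an unmeasured binary confounder with prevalence p1 in exposed and p0 in unexposed patients and relative risk RR, the bias factor is [1 + p1(RR − 1)] / [1 + p0(RR − 1)].
- p1 = 4%, p0 = 2%, RR = 2: 1.04/1.02 = 1.02.
- Same RR, p1 = 4%, p0 = 0: 1.04/1.00 = 1.04.
- Same RR, prevalences reversed (2% against 4%): 1.02/1.04 = 0.98.

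These values show the order of magnitude under those assumptions only.

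**The case against.** The strongest reply is that the list is provisional. It is labelled exemplar, the SAP will finalise it, and Table 6 variables are only considered for the PS (sections 10.3.3 and 10.7.1.1). This stands to the extent that the protocol does not fix a defective PS; the problem arises if the codes carry over. It does not dispose of the point, because these are printed codes that conflict with other printed codes, and section 10.3 makes them the starting point for country adaptation.

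Second, the protocol does not print the ICD-10 titles of D82.3 and B16. That stands too. The document shows that D82.3 is in a block it labels immunodeficiencies, and that hepatitis B lacks the chronic counterpart given for hepatitis C. How rarely D82.3 is recorded, and exactly what B16 covers, must be checked in the ICD-10 2019 version that section 10.3 adopts.

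Third, section 10.3.3.1 separately mentions chronic infections as relevant to inflammatory status, so chronic hepatitis B might be picked up there. No codes are listed for that item, so this is possible but not shown.

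Fourth, an all-zero covariate adds nothing to a PS, so deleting C46 changes no score, match or HR. That is correct. The benefit of that deletion is honest reporting.

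A reader might infer that none of the three viruses can be identified, or that the plan leaves oncogenic viruses uncontrolled as a class. The documents do not support either. Only the C46 row is provably empty, hepatitis B is partly captured, and four rows are untouched.

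**Conclusion.** The point holds as a correction to the code list. The C46 row contradicts the cohort's own exclusion criterion and is empty by construction. This assumes that the exclusion uses the overall Table 15 range C00-C96, as its wording implies; C46 is in none of the haematological, solid or skin sub-lists. The Epstein-Barr row is misplaced on the protocol's own labelling, and the hepatitis B row is incomplete by comparison with hepatitis C.

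A reader might also infer that the primary malignancy HR is materially biased. That is not supported: the protocol gives no prevalence or relative risk for these infections, so the effect cannot be computed. Under the assumed inputs above the bias factor runs from 0.98 to 1.04, against a study sized to detect an HR of 1.5. The effect is probably small. What is gained is that the viruses listed as confounders are measured, or are openly declared unmeasured.

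**What to change.** In Table 22, before the SAP and country code lists are finalised:

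1. Delete the C46 row, or state that Kaposi's sarcoma herpesvirus is not measured in this cohort.
2. Replace D82.3 with a code for Epstein-Barr virus infection.
3. Add the chronic hepatitis B codes and, where a source records it, carrier status. The HTLV-I row already uses a code of the Z22 type (Z22.6).
4. Check each replacement against the ICD-10 2019 version named in section 10.3 and against each country's adaptation.
5. Check every PS covariate against the exclusion criteria, as was done for Table 20. Leave structurally empty covariates out of the PS and do not report them as balanced.

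The cost is a short edit to an exemplar list and a note in the balance-table specification. It needs no new data and no change to design, sample size or timelines.

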8.4 Malignancies and knowledge gaps

Published studies have identified an increased frequency of some malignancies among patients with SLE, particularly for non-Hodgkin's lymphoma, leukaemia, and cancer of the vulva, lung, thyroid, and liver [13]. Although there is a decreased risk of other select types of cancer in patients with SLE, the overall cancer risk in SLE is slightly greater as compared with the general population [13]. Possible pathways linking SLE and malignancies include inherent immune system abnormalities, SLE medication exposures, interactions between medication and viral exposure, co-existing conditions (such as Sjögren's syndrome) and presence of "traditional" risk factors for malignancy (such as smoking, obesity and reproductive history) [10, 52, 59, 103].

Treatments that induce immune suppression may impair immune surveillance and thereby increase the risk for initiation or growth acceleration of malignancies. Furthermore, Type 1 IFNs may play a role in tumour surveillance. Therefore, while blocking type 1 IFN might be beneficial in controlling autoimmune diseases, the same pathway of suppression could potentially increase the risk of malignancies.

The impact of treatment with anifrolumab on the potential risk of malignancies is not known. In the placebo-controlled clinical trials, at any dose, malignant neoplasms (including non-melanoma skin cancers) were reported in 1.3% patients receiving anifrolumab, compared to 0.6% patients receiving placebo [92]. Malignancies excluding non-melanoma skin cancers were observed in 0.7% and 0.6% of patients receiving anifrolumab and placebo, respectively. In patients receiving anifrolumab, breast and squamous cell carcinoma were observed in more than one patient [92].

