10.7.1 Statistical methods

10.7.1.1 Time-based exposure sets and propensity score matching

Base cohort

The base cohort will be defined using SLE diagnosis within the study period as the inclusion criteria. Anifrolumab exposed patients in the base cohort will consist of individuals who had prior exposure to SLE SOC drugs. Hence, the base cohort will be formed of all patients who have used SLE SOC, some adding-on anifrolumab as incident user, and the others continuing SLE SOC alone.

Time-based exposure sets

Time-based exposure sets will be defined to determine the time-points at which comparability will be established. Time on SLE SOC (i.e., time from the first prescription of SLE SOC for moderate to severe SLE) will be considered as a marker of disease course. For each exposed patient, a time-

based exposure set will be created including all unexposed patients with similar time on SOC as the exposed at the time of anifrolumab initiation. Anifrolumab and SLE SOC prescriptions dates will be used to anchor the exposure sets from the base cohort [88]. The detailed process of time-based exposure set creation is presented in Section 10.1 and in Section 10.2.2.1.

Time-conditional propensity score-based matching

Time-conditional propensity scores will be used to compute, for each patient in each time-based exposure set, the propensity of being exposed to anifrolumab (vs. staying on SLE SOC) as a function of patient characteristics at the exposure risk set date. Variables identified as potential confounders included in Table 6 will be considered for inclusion in the time-conditional propensity score. The steps involved in creation of time-based exposure sets and PS matching are below:

- 1. In the base cohort, each patient is treated as a possible comparator in the beginning until exposure of anifrolumab or censoring due to other reasons.
- 2. The index date for patients in the exposed group is their anifrolumab first exposure date.
- 3. On a timescale of time since start of SLE SOC, for each timepoint where a patient is exposed to anifrolumab, the set of eligible comparators is formed based on time since the start of SLE SOC.

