• Most malignancies have long latency periods in the absence of immunosuppression [66]. Although immunosuppression shortens the latency period [100], current study follow-up time may be short (seven years will be the maximum duration between first enrolled patient and the end of follow-up) to identify some malignancies. Thus, the incidence may be underestimated. However, haematological malignancies are expected to be the most frequent cancer types among SLE patients [12, 13, 84]. For those, latency periods are likely to be shorter.

• Previous research suggests that biologics are associated with an increased risk of malignancies [100]. Therefore, cancer screenings (e.g., for breast or cervical cancers) and closer surveillance may be reinforced among patients exposed to biologics, namely anifrolumab [16]. If so, anifrolumab patients may have a diagnosis at an earlier time point than it would have been if it had been diagnosed by its clinical appearance. This may result in an increased risk of malignancy in anifrolumab patients. However, patients exposed to SLE SOC may also be exposed to other biologics or known carcinogenic drugs (such as cyclophosphamide) which may result in similar adherence to cancer screenings, minimising surveillance bias [41].

Capturing malignancies using claims data may be prone to misclassification because unconfirmed cases may be captured. Since no population-based cancer registry is used for France (SNDS), Germany (SHI) and Spain (SIDIAP), misclassification may occur. Additionally, in France, malignancies are only captured for patients that were hospitalised. Although virtually all patients may be hospitalised at some stage of the disease, under-detection may occur.

SLE severity and activity

• Disease severity and activity scales (e.g., Systemic Lupus Erythematosus Disease Activity Index 2000 [SLEDAI-2K score]) are frequently used in randomised controlled trials but are not routinely recorded in secondary data sources and therefore were not included. Activity could also be addressed by considering specific biomarkers (e.g., C3, C4) which are unlikely to be systematically used and available. To minimise the lack of available data, severity and activity algorithms that were previously defined [39, 56] will be used, incorporating information that is used in routine practice: scale-up of SLE treatment strategies, SLE clinical manifestations and HRU.

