Calcium channel blockers		x	C08
Cisplatin		x	L01XA01
Corticosteroids for systemic use, except SLE-related	х	x	H02, H02A, H02B, except the ones provided in Table 14
Diuretics		x	C03
Anti-inflammatory and antirheumatic products		x	M01A, M01B, M01C
Doxorubicin		x	L01DB01
Drugs used in diabetes		x	A10
Etoposide in combination with cisplatin and bleomycin		x	L01CB01; L01DC01
Hypnotics and sedatives, Anxiolytics		x	N05C, N05B
Immunostimulants	х		L03
Immunosuppressive agents except SLE- related	x		L04, L04A, L04AA, L04AX, except the ones provided in Table 14
Intrauterine and intravaginal hormonal contraceptives		x	G02BB, G02BA03
Lipid modifying agents (including statins)		x	C10
Methylhydrazines (procarbazine) (excluding nitrogen mustard, vincristine, procarbazine and prednisone and other combined chemotherapy including alkylating agents)		x	L01XB (excluding L01XB01; L01AA)
NSAIDs for systemic use		x	M01A
Other Carcinogenic drugs (e.g., Pioglitazone, Reserpine, Metronidazole, Chloroform, etc.) *		X	A10BG03, A10BD09, A10BD12, A14A, C02AA02, C02LA01, C02LA51, C02LA71, C02AA52, C04AX02, D01AE13, D05AD02, G04BX06, H03BA02, J01BA01, G01AA05, D10AF03, D06AX02,

Comedication	SI	Malignancies	ATC codes
			S01AA01, S02AA01, S03AA08, J01EB08, A01AB17, D06BX01, G01AF01, J01XD01, P01AB01, N01AB02, N02BE03, N02BE53, N02BE73, N03AB02, N03AB52, P03AX03, V10XA, V09XA
Podophyllotoxin derivatives (etoposide and teniposide)		х	L01CB
Sex hormones and modulators of the genital system		х	G03
Tamoxifen		x	L02BA01

Note: codes for "L01 – Antineoplastics" are unlikely to be present considering these are mainly administrated to cancer patients who are excluded of the cohort.

*As defined by the American Cancer Society [3].

Abbreviations: ATC, anatomical therapeutic chemical; NSAIDs, non-steroidal anti-inflammatory drugs; SI, serious infections; SLE, systemic lupus erythematosus.

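### Table 24 assigns non-SLE immunosuppressants to the serious infection cohort only, so as written they are not propensity-score candidates for the malignancy cohort

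*Protocol*

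**What the plan says.** Appendix 3, Table 24 has one column for serious infections and one for malignancies. The row "Immunosuppressive agents except SLE- related", with codes "L04, L04A, L04AA, L04AX, except the ones provided in Table 14", is marked under serious infections and blank under malignancies. The neighbouring row "Corticosteroids for systemic use, except SLE-related" is marked under both.

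Table 24 feeds the analysis by two links. Table 6 (Section 10.3.3) lists "Comedication [polypharmacy] (Table 24") as a covariate for both cohorts. Section 10.7.1.1 then states: "Variables identified as potential confounders included in Table 6 will be considered for inclusion in the time-conditional propensity score".

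On cancer risk, Section 8.4 says: "Treatments that induce immune suppression may impair immune surveillance and thereby increase the risk for initiation or growth acceleration of malignancies". Section 10.9 says: "Previous research suggests that biologics are associated with an increased risk of malignancies". Also in Section 10.9, under outcome assessment for both outcomes, the protocol warns that more prior immunosuppressant exposure among anifrolumab patients would produce an apparent excess risk. Its remedy is to put the type and duration of prior SLE standard of care into the propensity score. Section 10.3.3.1, on malignancy confounders, adds: "Within the group of other immunosuppressants, recognised carcinogenic drugs will be considered separately".

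**The concern.** The protocol treats immune suppression as a possible cause of cancer and names imbalance in prior immunosuppressants as a route to a spurious signal. Its covariate table nevertheless leaves one group of immunosuppressants out of the malignancy cohort and keeps it for infections. The remedy in Section 10.9 covers SLE standard of care, so it does not reach drugs outside Table 14.

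At stake is the comparison in primary objective 2. If prior use of non-SLE immunosuppressants differs between anifrolumab initiators and their matched comparators, and if these drugs affect cancer risk, the malignancy hazard ratio carries that difference. Section 10.7.1.4 adds variables found imbalanced after matching to the outcome model, but a drug group outside the malignancy covariate set may never be checked for balance.

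**Working it through.** The protocol gives no figure to reproduce on this point. The check is a reading of the tables followed by a bias calculation on assumed inputs.

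**Step 1: is the blank cell real?** Table 24 has 29 comedication rows. Twenty-seven are marked for malignancies and three for serious infections: non-SLE corticosteroids (both cohorts), immunostimulants (serious infections only) and non-SLE immunosuppressants (serious infections only). Since 27 + 3 - 1 = 29, every row is accounted for. The corticosteroid row shows that the table can mark both columns, so the blank is unlikely to come from text extraction.

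**Step 2: does another malignancy row bring these drugs in?** None of the 27 rows marked for malignancies carries an L04 code. That includes the row of other carcinogenic drugs.

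**Step 3: does Table 14 bring them in?** SLE standard of care (Table 14) is a covariate for both cohorts. It contains belimumab, rituximab, azathioprine, cyclophosphamide, cyclosporine, methotrexate, mycophenolate, tacrolimus, sirolimus, leflunomide, tofacitinib, baricitinib and others, but no anti-TNF agent. The gap is therefore L04 drugs outside Table 14.

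**Step 4: does Section 10.3.3.1 close the gap?** Its sentence on other immunosuppressants can be read in two ways. If it refers to Table 14 drugs, the non-SLE agents stay uncovered. If it refers to the Table 24 group, it conflicts with the blank cell. Neither reading supplies a code for the malignancy cohort.

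**Step 5: are the data available?** Table 26 lists prior exposure to immunosuppressive drugs as available in all four sources (in Spain, except when given during hospitalisation).

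**Step 6: how large could the bias be?** The protocol gives neither the prevalence of use nor a relative risk, so these are assumptions: prior use p1 of 10-20% in anifrolumab patients, p0 of 5-10% in comparators, and relative cancer risk RR of 1.5-2.0. For one unadjusted binary confounder,

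bias factor = (1 + p1(RR - 1)) / (1 + p0(RR - 1)).

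| p1 | p0 | RR 1.5 | RR 2.0 |
|---|---|---|---|
| 0.10 | 0.05 | 1.050/1.025 = 1.02 | 1.10/1.05 = 1.05 |
| 0.10 | 0.10 | 1.00 | 1.00 |
| 0.20 | 0.05 | 1.100/1.025 = 1.07 | 1.20/1.05 = 1.14 |
| 0.20 | 0.10 | 1.100/1.050 = 1.05 | 1.20/1.10 = 1.09 |

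The range is 1.00 to 1.14. At the top end, a true hazard ratio of 1.00 would be estimated near 1.14. If prior use were higher in comparators, the bias would run the other way: with p1 = 0.05, p0 = 0.20 and RR = 2.0 the factor is 1.05/1.20 = 0.875.

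**The case against.** **The list is provisional.** Table 24 is an exemplar, Appendix 3 leaves the final code lists to the SAP, and Section 10.3.3 leaves the final choice of confounders to data availability and clinical relevance. This makes the point easy to correct, but it does not remove it. The protocol states a cohort assignment that conflicts with its own reasoning, and a SAP that follows it carries the gap forward.

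**Most of the relevant exposure is already covered.** This largely stands. Patients reaching anifrolumab after several lines will mainly have had Table 14 drugs, and Section 10.3.1.1.2 describes that list as covering what moderate and severe SLE patients could receive. A reader might infer from Table 24 that immunosuppressants in general are missing from the malignancy score. The documents do not support that: Table 14 drugs are covariates in both cohorts and non-SLE corticosteroids are marked for malignancies.

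**Other autoimmune diseases act as a proxy.** Partly. Section 10.3.3.1 names them as malignancy confounders, and Table 20 includes psoriasis, inflammatory bowel disease and multiple sclerosis. Its autoimmune codes include no M05 or M06 code for rheumatoid arthritis, however, and a diagnosis does not show who received the drug.

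**The imbalance is not documented.** This stands. A reader might infer that the omission will inflate the hazard ratio for anifrolumab. Nothing in the protocol says that anti-TNF or similar use is commoner in initiators than in comparators matched on standard-of-care duration and propensity score.

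**The remark on biologics comes from a passage about cancer screening and surveillance.** Also correct. It shows that the sponsor regards biologics as relevant to cancer risk, not that the drugs in the Table 24 row carry a particular excess.

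**Conclusion.** The point holds for non-SLE immunosuppressants only. As written, they are propensity-score candidates for serious infections and not for malignancies, against the rationale in Sections 8.4 and 10.9 and with an unresolved sentence in Section 10.3.3.1.

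The size cannot be derived from the protocol. The factor of 1.00 to 1.14 rests wholly on the assumed prevalences and relative risks. It also treats the confounder as wholly unadjusted, whereas matching on correlated covariates would probably remove part of the bias. Even the top of the range is well below the hazard ratio of 1.5 used for study size, so this is a modest source of residual confounding. The change is still worth making, because the exposure is recorded, its codes are already specified for the other cohort, and the protocol's own argument calls for it.

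**What to change.** - In Table 24, mark the non-SLE immunosuppressant row for malignancies as well, or state why it is left out.
- Enter it in the malignancy propensity score as a single prior-use covariate and report its balance before and after matching.
- Align Section 10.3.3.1 with Table 24, so that it is clear which drugs the sentence on other immunosuppressants means and which codes identify them.
- Split by class only where counts allow. Table 8 expects 183 anifrolumab patients in Denmark and 216 in Germany for the malignancy cohort. At the assumed 10-20% use this gives about 18 to 37 users (183 × 0.10 and 183 × 0.20) and 22 to 43 users (216 × 0.10 and 216 × 0.20), which is thin for several indicators.
- Use the look-back that each source supports. Section 10.4.1 describes Danish hospital medication from May 2018, no German inpatient medication, and French hospital drugs only when they are on the high-cost list.

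The cost is one table cell, a clarifying sentence and a line in the SAP, with no new code list. The downside is one more covariate that may be sparse in the smaller data sources.
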